5.0 PATIENT EVALUATION FLOWSHEET: PRE-TREATMENT, ON STUDY, AND AFTER TREATMENT

All patients entered on study must be evaluated according to the schedule outlined below with documentation submitted according to the schedule in Appendix IV.

Required Investigations	Pre-study (≤ 7 days prior to registration)	Day 1 each cycle, and as clinically indicated	Day 1 every 12 weeks	4 weeks after completion of protocol therapy	3 month follow-up (only required for pts without confirmed PD and ongoing toxicities ¹)
History and Physical Exam					
Including: height and weight, ECOG performance status, documentation of all measurable and non- measurable disease, clinical tumour measurements (if applicable); Vital signs ² : blood pressure, heart rate, temperature	Х	Х		Х	
Laboratory Procedures/Assessments ³					
CBC, neutrophils, lymphocytes , platelets	Х	Х		X^4	X ⁴
PTT, PT/INR (if on anticoagulants)	Х	Х		X^4	X^4
Serum creatinine, creatinine clearance (calculated), electrolytes (calcium, potassium, magnesium) bilirubin, ALP, AST, ALT, LDH, albumin, glucose, amylase ⁵ , lipase ⁵ , TSH ⁶	х	Х		X^4	X ⁴
Pregnancy Test ⁷	Х	X^8			
Radiology					
Tumour Imaging (Chest, abdomen and pelvis scan; other scans as necessary to document disease) Bone scan for osteosarcoma patients	within 28 days prior to registration or 35 if negative		X9	X^{10}	X^{10}
Other Investigations			-	-	-
Tumour markers (i.e. CA-125, etc.) ¹¹ if applicable	Х				
LVEF ¹²	(within 28 days prior to registration)	on alimically indicated			
Urinalysis (dipstick – including protein, specific gravity, glucose and blood)	Х				
Archival Tumour Tissue for assessment of TILs and PD-L1 expression (pre-screening – cohort #2 only)	X ¹³				
Correlative Studies Blood Collection	X ¹⁴		See Sect	ion 12.0 for det	ails
Adverse events	Х	Continuo	usly	X^1	

footnotes on next page ...

- Every three months thereafter to follow adverse events felt related until resolved to \leq Grade 2. Adverse Events to be evaluated using the NCI Common Terminology Criteria for Adverse Events (CTCAE v4.0) (see Appendix V).
- 2 Patients will be monitored before, during and after the first cycle infusion of tremelimumab and durvalumab with assessment of vital signs to be collected \leq 30 minutes prior to start of infusion then every 30 ±5 minutes during infusion; a 1-hour observation period is recommended after the tremelimumab. Assessment of vital signs in subsequent cycles is required prior to the start of the infusion, and then as clinically indicated. If no clinically significant infusion reactions are observed during or after the first cycle of tremelimumab+durvalumab therapy, subsequent infusion observation periods can be at the investigator's discretion.
- 3 Pre-treatment blood draws and physical exams may be done one working day prior to treatment if necessary (e.g. Friday for treatment on Monday, or to accommodate holidays). In order to ensure that nadir counts are not missed, every effort should be made to do interim blood draws within 24 hours of the day specified in the protocol. If a patient shows an AST or ALT ≥3 x ULN together with total bilirubin ≥2 x ULN, refer to Appendix II for further instructions on cases of increases in liver biochemistry and evaluation of Hy's Law. These cases should be reported as SAEs if, after evaluation, they meet the criteria for a Hy's law case or if any of the individual liver test parameters fulfill any of the SAE criteria.
- 4 Required at 4 weeks. To be done additionally every 3 months thereafter to follow abnormal lab results felt related until resolved to \leq Grade 2.
- 5 It is preferable that both amylase and lipase are assessed. For sites where only 1 of these parameters is routinely measured then either lipase or amylase is acceptable.
- 6 Free T3 and free T4 will be measured if TSH is abnormal.
- 7 For women of childbearing potential only (urine or serum test). Within 72 hours prior to registration. Pregnancy test (in women of childbearing potential), as part of Pre-Study Evaluation, may include an ultrasound to rule-out pregnancy.
- 8 As clinically indicated in WOCBP
- 9 To ensure comparability, baseline scans and subsequent scans to assess response must be performed using identical technique (i.e. scans performed immediately following bolus contrast administration using a standard volume of contrast, the identical contrast agent, and preferably the same scanner). Maintain schedule every 12 weeks even if cycles are delayed. For osteosarcoma patients, every 3 months if bone mets are present at baseline. For patients remaining on study beyond January 2022, the frequency of imaging assessment may be reduced to every 6 months at the description of the investigator and discussion with CCTG.
- 10 To be done every 12 weeks until relapse or progression (iCPD) for up to 2 years, for patients with CR/iCR, PR/iPR, SD/iSD response as defined in Section 8. Patients with CR/iCR or PR/iPR or equivocal PD (pseudoprogression)/iUPD should have scans repeated after 4 weeks, but no more than 8 weeks, to confirm response.
- 11 Depending on histology, applicable markers (i.e. CA-125 for the Clear Cell Carcinoma of the Ovary cohort) must be reported as per standard of care at local sites.
- 12 Only if significant cardiac history (see section 4.2.6).
- 13 Must be confirmed available prior to registration on ALL patients. Archival tissue submission should be sent at the same time that the baseline CRF is submitted for each patient. Prescreening of TIL and PDL1 expression is required for cohort 2 patients prior registration. See Section 12.0 for details.
- 14 After registration but before the first dose of study treatment. See lab manual for details.

5.1 Follow-up for Ineligible or Patients That Go Off Study Prior to Starting Protocol Therapy

The follow-up requirements for ineligible patients/patients who have received no protocol therapy prior to going off study include submission of the Baseline Report plus an End of Treatment Report. Data submission for ineligible participants who have received at least one dose of protocol therapy should be followed according to the protocol to allow for treatment and adverse event assessment.

6.0 ENTRY/REGISTRATION PROCEDURES

6.1 Entry Procedures

All registrations will be done through the CCTG web-based, password-operated Electronic Data Capture (EDC) system. Complete details regarding obtaining a password, accessing the system and registering patients will be provided at the time of study activation and are also available in the "EDC Data Management Guidebook", posted on the IND.228 trial specific web-site. If sites experience difficulties accessing the system and/or registering/randomizing patients please contact the help desk (link in EDC) or the IND.228 Study Coordinator.

All eligible patients enrolled on the study by the participating treatment centre will be assigned a serial number which must be used on all documentation and correspondence with CCTG.

The following information will be required:

- trial code (CCTG IND.228)
- patient's initials (may be coded)
- informed consent version date, date signed by patient, name of person conducting consent discussion and date signed
- confirmation of the requirements listed in Section 4.0, including dates of essential tests and actual laboratory values

6.2 Registration

Registration will be provided electronically.

Note: The validity of results of the trial depends on the authenticity of and the follow-up of all patients entered into the trial. Under no circumstances, therefore, may an allocated patient's data be withdrawn prior to final analysis, unless the participant withdraws from the trial and requests that data collection/submission cease from the point in time of withdrawal.

All eligible patients admitted to the trial will be followed by the coordinating centre. It is the responsibility of the physician in charge to satisfy himself or herself that the patient is indeed eligible before requesting registration.

All registered patients are to be followed until death or until sites are informed by CCTG that further follow-up is no longer required. The follow-up requirements for ineligible patients are outlined in Section 5.1.

The follow-up requirements for ineligible patients who have received no protocol therapy include submission of the Baseline Report only. Data submission for ineligible participants who have received at least one dose of protocol therapy should be followed according to the protocol to allow for treatment and adverse event assessment.

7.0 TREATMENT PLAN

Although the Canadian Cancer Trials Group acts as the coordinating agency for the trial, the responsibility for treatment of patients rests with the individual investigator.

In accordance with CCTG policy, protocol treatment is to begin within 2 working days of patient registration.

7.1 Durvalumab and Tremelimumab Treatment Plan

7.1.1 Drug Administration

When durvalumab is given with tremelimumab, tremelimumab will be administered first. Durvalumab infusion will start approximately 1 hour after the end of tremelimumab infusion.

One cycle will be defined as 4 weeks. Tremelimumab will only be given for the first 4 cycles.

Agent(s)	Dose	Route	Duration	Schedule
Durvalumab	1500 mg	IV	60 min	Day 1 every 4 weeks
Tremelimumab	75 mg	IV	60 min	Day 1, cycles 1-4

Patients with a body weight of less than or equal to 30kg should be dosed using a weight based dosing schedule. See Section 3.3.

7.1.2 Premedication

No routine premedication (e.g. for nausea) or prophylaxis for hypersensitivity is required. Management of symptoms should take place as necessary (See Appendix II). Premedication is not expected to be required. See Appendix II with respect to premedication of patients that have had a prior \leq Grade 2 infusion-related reaction. Details of any premedication or concomitant medication given to manage or prevent adverse events should be recorded on the electronic case report form (eCRF).

7.1.3 *Patient Monitoring*

Patients will be monitored before, during infusion and after the infusion of tremelimumab and durvalumab with assessment of vital signs as specified in Section 5.0. A 1-hour observation period is recommended after the first infusion of durvalumab and tremelimumab. If no clinically significant infusion reactions are observed during or after the first cycle, subsequent infusion observation periods can be at the Investigator's discretion (suggested 30 minutes after each durvalumab and tremelimumab infusion).

Guidelines for management of infusion-related reaction are summarized in Appendix II.

All patients should be closely monitored according to guidelines in Section 5.0 and be advised to contact the treating centre in the case of significant toxicities.

7.1.4 *Dose Modifications*

The major toxic effects of durvalumab or tremelimumab which are anticipated to limit dosing are hypersensitivity/ infusion related reactions and possible class related immune related AEs, based on the mechanism of action of durvalumab and tremelimumab leading to T-cell activation and proliferation. Potential immune related AEs include pneumonitis, hepatitis, diarrhea/colitis and intestinal perforation, endocrinopathies (thyroiditis, hypo and hyperthyroidism, adrenal insufficiency, hypophysitis/hypopituitarism diabetes insipidus and Type 1 diabetes mellitus), nephritis, rash/dermatitis, pancreatitis, myocarditis, myositis/polymyositis and rare/less frequent irAEs including neuromuscular toxicities such as myasthenia gravis and Guillain-Barre syndrome. Other inflammatory responses that are rare with a potential immune-mediated etiology include, but are not limited to, pericarditis, sarcoidosis, cholangitis sclerosing, cystitis, uveitis and other events involving the eye (e.g. keratitis and optic neuritis), skin (e.g. scleroderma, vitiligo and pemphigoid), hematological (e.g. hemolytic anemia, immune-mediated neutropenia and immune thrombocytopenic purpura) and rheumatological (e.g. polymyalgia rheumatic and autoimmune arthritis) events, vasculitis, non infectious encephalitis or non infectious meningitis. It is possible that events with an inflammatory or immune mediated mechanism could occur in nearly all organs.

The guidelines which follow outline dose adjustments for several of these toxic effects. If a patient experiences several adverse events and there are conflicting recommendations, please use the recommended dose adjustment that requires the greatest dose hold or discontinuation. Adverse events will be graded using the NCI Common Terminology Criteria for Adverse Events (CTCAE) (see Appendix V).

Dose adjustments (slowing/interruption of infusion rate, omission of a dose, or permanent discontinuation) will be made for hematologic and other adverse events.

If the infusion cannot be administered, it should be omitted until the next planned infusion.

The next cycle should not be given until the laboratory criteria in Section 4.1.7 are met and resolution of all drug related toxicity to \leq grade 2. Discuss with CCTG if asymptomatic/not felt to be clinically significant.

7.1.5 Management of Toxicity

Please refer to detailed toxicity management guidelines in Appendix II.

All dose modifications should be documented with clear reasoning and documentation of the approach taken.

7.1.6 Management of Infusion Reactions

Guidelines for management of infusion-related reaction are summarized in Appendix II. The standard infusion times for both durvalumab and tremelimumab are 1 hour. However, if there are interruptions during infusion, the total allowed time should not exceed 8 hours at room temperature.

Study personnel must be trained to recognize and treat anaphylaxis. The study site must have immediate access to appropriate drugs and medical equipment to treat acute anaphylactic reactions, emergency resuscitation teams and equipment in addition to the ability to admit patients to an intensive care unit if necessary.

7.1.7 Dose Adjustments for Immune Related Adverse Events and Other (Non-Immune Related) Adverse Events Related to Study Therapy

Guidelines for dose modification and toxicity management of immune related and non-immune related adverse events are summarized in Appendix II.

Centres must contact CCTG in the event of severe event(s), especially when the use of drugs such as infliximab are considered.

7.2 Duration of Therapy

Treatment with durvalumab \pm tremelimumab (to a maximum of 4 doses, cycles 1-4) will continue until disease progression or unacceptable toxicity.

Exceptions to the duration of treatment for patients with continued response may be made after consultation with CCTG.

7.3 Patient Compliance

Treatment compliance will be monitored by drug accountability, as well as recording drug administration in the patient's medical record and case report form (CRF).

7.4 Concomitant Therapy

Details of any concomitant medications (prescription, non-prescription, or over-the-counter medications) taken by the patient at study entry and during protocol therapy must be recorded on the appropriate electronic case report forms (eCRFs).

7.4.1 Permitted

- Growth factors may be used according to centre policy to treat life threatening toxicity but cannot be used in place of protocol defined dose adjustments. Please consult CCTG senior investigator in the case of patients experiencing multiple delays as exceptions may be made for patients who are benefitting from protocol therapy.
- Other supportive and palliative care (e.g. pain control) as required throughout the study.
- Anti-emetics or anti-diarrheal agents as required.

7.4.2 Not Permitted

- Cytokines;
- Other anti-cancer treatment;
- Other investigational therapy;
- Concurrent radiation treatment; (Note: if patients require palliative radiation or prophylactic radiation (e.g. of brain) consult CCTG for exception to this rule; protocol therapy will need to be held prior to and during the radiation).
- Corticosteroids IV or PO (except for the treatment of ≥ grade 3 infusion reaction, treatmentrelated toxicity (See Appendix II), and nausea prophylaxis for chemotherapy). Note: Topical applications (e.g. rash), inhaled sprays (e.g. obstructive airways diseases), eye drops or local injections (e.g. intra-articular) are allowed. Patients who are on low oral doses of prednisone (5 mg BID or dexamethasone equivalent) must discontinue prior to study entry unless medically contraindicated.
- Live attenuated vaccines within 30 days of durvalumab dosing (i.e. 30 days prior to the first dose, during treatment with durvalumab and for 30 days post discontinuation of durvalumab. Inactivated vaccines, such as the injectable influenza vaccine, are permitted.

8.0 CRITERIA FOR MEASUREMENT OF STUDY ENDPOINTS

8.1 Definitions

8.1.1 Evaluable for Adverse Events

All patients will be evaluable for adverse event evaluation from the time of their first treatment.

8.1.2 *Evaluable for Response*

All patients who have received at least one cycle of therapy and have their disease re-evaluated will be considered evaluable for response (exceptions will be those who exhibit objective disease progression prior to the end of cycle 1 who will also be considered evaluable). Patients on therapy for at least this period and who meet the other listed criteria will have their response classified according to the definitions set out below *[Seymour 2017]*.

Response and progression will be evaluated in this study using the revised international criteria (1.1) proposed by the RECIST (Response Evaluation Criteria in Solid Tumours) committee as well as the modified iRECIST guidelines *[Seymour 2017]*. Investigators should note the different requirements for confirmatory scans as well as follow up for the two criteria.

8.2 Response and Evaluation Endpoints

Response and progression will be evaluated in this study using the revised international criteria (1.1) proposed by the RECIST (Response Evaluation Criteria in Solid Tumours) committee as well as the Immune-Related modified RECIST. Investigators should continue treatment, as appropriate, in the absence of unacceptable toxicity, until unequivocal disease progression. This is particularly important for patients in whom pseudoprogression may have occurred. Follow up response assessments must be continued until unequivocal disease progression has occurred.

8.2.1 Measurable Disease

Measurable tumour lesions (nodal, subcutaneous, lung parenchyma, solid organ metastases) are defined as those that can be accurately measured in at least one dimension (longest diameter to be recorded) as ≥ 20 mm with chest x-ray and as ≥ 10 mm with CT scan or clinical examination. Bone lesions are considered measurable only if assessed by CT scan and have an identifiable soft tissue component that meets these requirements (soft tissue component ≥ 10 mm by CT scan). *Malignant lymph nodes* must be ≥ 15 mm in the short axis to be considered measurable; only the short axis will be measured and followed. All tumour measurements must be recorded in millimetres (or decimal fractions of centimetres). Previously irradiated lesions are not considered measurable unless progression has been documented in the lesion.

8.2.2 Non-measurable Disease.

All other lesions (or sites of disease), including small lesions are considered non-measurable disease. Bone lesions without a measurable soft tissue component, leptomeningeal disease, ascites, pleural/pericardial effusions, lymphangitis cutis/pulmonis, inflammatory breast disease, lymphangitic involvement of lung or skin and abdominal masses followed by clinical examination are all non-measurable. Lesions in previously irradiated areas are non-measurable, unless progression has been demonstrated.

8.2.3 Target Lesions

When more than one measurable tumour lesion is present at baseline all lesions up to a maximum of 5 lesions total (and a maximum of 2 lesions per organ) representative of all involved organs should be identified as target lesions and will be recorded and measured at baseline. Target lesions should be selected on the basis of their size (lesions with the longest diameter), be representative of all involved organs, but in addition should be those that lend themselves to reproducible repeated measurements. Note that pathological nodes must meet the criterion of a short axis of ≥ 15 mm by CT scan and only the short axis of these nodes will contribute to the baseline sum. All other pathological nodes (those with short axis ≥ 10 mm but < 15 mm) should be considered non-target lesions. Nodes that have a short axis < 10 mm are considered non-pathological and should not be recorded or followed (see 8.2.4). At baseline, the sum of the target lesions (longest diameter of tumour lesions plus short axis of lymph nodes: overall maximum of 5) is to be recorded.

After baseline, a value should be provided on the CRF for all identified target lesions for each assessment, even if very small. If extremely small and faint lesions cannot be accurately measured but are deemed to be present, a default value of 5 mm may be used. If lesions are too small to measure and indeed are believed to be absent, a default value of 0 mm may be used.

8.2.4 Non-target Lesions

All non-measurable lesions (or sites of disease) plus any measurable lesions over and above those listed as target lesions are considered non-target lesions. Measurements are not required but these lesions should be noted at baseline and should be followed as "present" or "absent".

8.2.5 Response.

All patients will have their BEST RESPONSE from the start of study treatment until the end of treatment classified as outlined below:

All patients will have their BEST RESPONSE from the start of study treatment until the end of treatment classified as outlined below:

Complete Response (CR): disappearance of *target* and *non-target* lesions and normalization of tumour markers. Pathological lymph nodes must have short axis measures < 10mm (Note: continue to record the measurement even if < 10mm and considered CR). Residual lesions (other than nodes < 10mm) thought to be non-malignant should be further investigated (by cytology specialized imaging or other techniques as appropriate for individual cases [ref RECIST 1.1]) before CR can be accepted. Confirmation of response is only required in non-randomized studies.

Partial Response (PR): at least a 30% decrease in the sum of measures (longest diameter for tumour lesions and short axis measure for nodes) of target lesions, taking as reference the baseline sum of diameters. Non target lesions must be non-PD. Confirmation of response is only required in non-randomized studies. Patients with CR/iCR or PR/iPR should have scans repeated after 4 weeks, but no more than 8 weeks, to confirm response.

Stable Disease (SD): Neither sufficient shrinkage to qualify for PR nor sufficient increase to qualify for PD taking as reference the smallest sum of diameters on study.

Progressive Disease (PD): at least a 20% increase in the sum of diameters of measured lesions taking as references the smallest sum of diameters recorded on study (including baseline) AND an absolute increase of > 5mm. Appearance of new lesions will also constitute progressive disease (including lesions in previously unassessed areas). In exceptional circumstances, unequivocal progression of non-target disease may be accepted as evidence of disease progression, where the overall tumour burden appears to have increased by at least 73% in volume or, in select instances where tumour burden has increased sufficiently to require urgent medical intervention (e.g. radiation for spinal cord compression or drainage of a fluid collection. Modest increases in the size of one or more non-target lesions are NOT considered unequivocal progression. If the evidence of PD is equivocal (target or non-target), treatment may continue until the next assessment, but if confirmed, the earlier date must be used.

Patients that are clinically well may continue on therapy following RECIST progression with new lesions or increase in target lesions if the increase in disease burden does not meet the definition of PD by immune response criteria [Seymour 2017]. In this situation, patients do not have unequivocal progression until immune response criteria are met (see Table 4 below).

T (I)		New *	Overall	Best Response for this
Target Lesions	Non-Target Lesions	Lesions*	Response	Category also Requires
Target lesions \pm non	i target lesions		[
CR	CR	No	CR	Normalization of tumour markers, tumour nodes <10mm
CR	Non-CR/Non-PD	No	PR	
CR	Not all evaluated	No	PR	
PR	Non-PD/ not all evaluated	No	PR	
SD	Non-PD/ not all evaluated	No	SD	documented at least once \geq 4 wks. from baseline
Not all evaluated	Non-PD	No	NE	
PD	Any	Any	PD	
Any	PD	Any	PD	
Any	Any	Yes*	PD	
Non target lesions C	ONLY			
No Target	CR	No	CR	Normalization of tumour markers, tumour nodes < 10mm
No Target	Non-CR/non-PD	No	Non-CR / non-PD	
No Target	Not all evaluated	No	NE	
No Target	Unequivocal PD	Any	PD	
No Target	Any	Yes*	PD	
evidence of dis for stopping th	sease progression at that time	me should be ve PD. Every	reported as "	ntinuation of treatment without objective symptomatic deterioration". This is a reason be made to document the objective

Table 3: Integration of Target, non-Target and New Lesions into Response Assessment:

progression even after discontinuation of treatment.

Investigators should record all new lesions; if the new lesion is felt to be equivocal, treatment may be continued pending further assessments - see table 5.

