13.2 Primary Endpoints and Analysis

Primary endpoint of this study is objective response rate, defined as the proportion of response evaluable patients who had complete response (CR) or partial response (PR) as their best response as assessed by RECIST version 1.1 criteria (i.e. a 30% decrease in the sum of the longest diameters of the target lesions maintained for at least 4 weeks (CR), or complete disappearance of disease and cancer related symptoms, also maintained for at least 4 weeks (CR)). Early progression is defined as progressive disease at or prior to the first assessment. The exact 95% confidence interval for the response rate will be calculated. The median and range of the duration of response, defined as the time from date of CR or PR to the date when progression or death is observed, will be estimated based on Kaplan-Meier method.

Sample Size for Each of 8 Disease Cohorts

Stage 1 of Accrual: 10 response evaluable patients will be entered in the first stage. Using response hypotheses of $H_0 \le 5\%$ and $H_a \ge 25\%$, we would reject the drug at the end of the first stage of accrual if no responses were seen. Otherwise, additional 10 patients will be accrued to the cohort.

Stage 2 of Accrual: Additional 10 response evaluable patients will be accrued. We would accept the drug as active if four or more responses are observed from 20 patients accrued.

Significance Level and Power: The procedure described above tests the null hypothesis (H0) that the response rate is 5% versus alternating hypotheses (H1) that the response rate is 25%. The significance level (i.e. the probability of rejecting H0 when it is true) is α =0.02 and the power (i.e. the probability of rejecting H0, i.e. deciding the regimen is active, when H1 is true) is 0.76. In addition, if the true response rate of an agent is 10%, it would be identified as ineffective with probability of 0.87. If the true response rate of the agent is 30%, it would be identified as effective with probability of 0.88.

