Since the eligibility will not initially be limited to patients with tumours expression of PD1/PDL1 and or TILs (with the exception of cohort 2); before closing the original cohort when no response was observed after the first stage of the accrual, where feasible, a minimum of 10 patients with tumours with TILs and/or PD-L1 expression will be included in the response analysis. This modified cohort may be expanded to the second stage of accrual if there is at least one response observed.

Accrual and Duration of Study

A minimum of 10 and maximum of 20 response evaluable patients per cohort will be accrued. Should a disease cohort meet or exceed its activity goal, and recruitment is not limiting, additional enrollment beyond 20 patients/cohort may be considered to improve the estimate of anti-tumour activity and exploration of biomarkers outcome correlations. Evidence of anti-tumour response in the first stage will lead to the implementation of *optional* fresh tumour biopsies in patients subsequently enrolled to allow for more detailed genomic analyses. If an unusually high level of activity is seen (i.e. > 4/10 patients with objective response) the data will be made available to AstraZeneca for regulatory submission.

Following a survey of the CCTG IND members, the minimum estimated recruitment is 10 patients/year/cohort. If after 2 years, fewer than 10 patients have been registered in any given disease cohort and no responses have been observed, that cohort will close to accrual due to lack of enrolment. The minimum number of patients recruited is estimated to be 70 and the maximum number is estimated to be 140, assuming some patients will be registered, while some cohorts will close early for inactivity or lack of accrual feasibility. The maximum number will be increased if there are cohorts which will be modified to include patients with TILs and/or PD-L1 expression or additional enrolment beyond 20 patients/cohort is considered.

Patients will be accrued from approximately 15 cancer treatment centres across Canada over a period of approximately 24-48 months.

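### The response-evaluable set in 8.1.2 leaves out treated patients who die or deteriorate before any disease re-evaluation, so the ORR in 13.2 is biased upward by a small, unreported amount

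*Combined protocol and SAP*

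**What the plan says.** Section 8.1.2 sets two joint conditions: "All patients who have received at least one cycle of therapy and have their disease re-evaluated will be considered evaluable for response". The only patients it adds back are these: "exceptions will be those who exhibit objective disease progression prior to the end of cycle 1 who will also be considered evaluable". Neither death nor symptomatic deterioration is named.

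Section 13.2 carries this set into the primary endpoint, which is "defined as the proportion of response evaluable patients who had complete response (CR) or partial response (PR) as their best response". It also states: "Early progression is defined as progressive disease at or prior to the first assessment". It does not say what role early progression plays in the denominator.

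The sample-size text mixes two units. Both stages are planned in response-evaluable patients, and the accrual paragraph says "A minimum of 10 and maximum of 20 response evaluable patients per cohort will be accrued". The success rule reads differently: "We would accept the drug as active if four or more responses are observed from 20 patients accrued". No rule for replacing non-evaluable patients is written.

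Section 8.2.5 says "All patients will have their BEST RESPONSE from the start of study treatment until the end of treatment classified as outlined below". Section 13.2 does not use that wider group for ORR, and no ORR on all treated patients is defined.

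**The concern.** A CR or PR in this trial has to be confirmed and held for at least 4 weeks (8.2.5 and 13.2). A patient with no assessment after baseline therefore cannot be a responder. Leaving such a patient out of the denominator removes a certain non-responder and can only push ORR up.

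The loss is foreseeable. The population has advanced cancer with no curative option and no cap on prior chemotherapy regimens (4.1.1, 4.1.6), and the first scheduled tumour imaging is at 12 weeks (5.0). ORR is the primary endpoint and the basis for calling the regimen active in each of eight small single-arm cohorts. A reader of the results would take ORR as a description of the patients who were treated. As defined, it describes those who reached a re-evaluation.

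**Working it through.** **Reproducing the design.** Inputs from 13.2: 10 patients in stage 1, stop if there are no responses, 10 more in stage 2, call active at 4 or more of 20.

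P(active | p) = sum over x = 1 to 10 of Bin(x; 10, p) × P(Bin(10, p) ≥ 4 − x)

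| True rate p | Computed P(active) | Plan |
|---|---|---|
| 5% | 0.0153 | 0.02 |
| 10% | 0.1285 | 1 − 0.87 = 0.13 |
| 25% | 0.7622 | 0.76 |
| 30% | 0.8830 | 0.88 |

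The plan's figures are right for 20 patients who share the response rate p.

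**Inflation of ORR.** Let d be the share of treated patients who are never re-evaluated and so excluded. None of them responds, so evaluable ORR = all-treated ORR / (1 − d). The documents give no d. I assume 5%, 10% and 20%: 1/0.95 = 1.05, 1/0.90 = 1.11, 1/0.80 = 1.25.

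**No replacement.** Take 20 treated patients and 4 responders, with exact (Clopper-Pearson) 95% intervals:

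| Dropped | ORR | 95% CI |
|---|---|---|
| 0 | 4/20 = 20.0% | 5.7 to 43.7% |
| 1 | 4/19 = 21.1% | 6.1 to 45.6% |
| 2 | 4/18 = 22.2% | 6.4 to 47.6% |
| 4 | 4/16 = 25.0% | 7.3 to 52.4% |

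The number of responders is unchanged, so the decision is unchanged. P(active) stays at 0.015 for a true 5% and 0.13 for a true 10%. Only the estimate and its interval move.

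**Replacement until 10 and then 20 are evaluable.** If the rates of interest are those of all treated patients, the same rule now operates at p/(1 − d):

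| d | True 5%: evaluable rate, P(active) | True 10%: evaluable rate, P(active) | True 10%: P(stage 1 stop) |
|---|---|---|---|
| 0 | 5.00%, 0.015 | 10.00%, 0.13 | 0.35 |
| 5% | 5.26%, 0.018 | 10.53%, 0.15 | 0.33 |
| 10% | 5.56%, 0.022 | 11.11%, 0.17 | 0.31 |
| 20% | 6.25%, 0.032 | 12.50%, 0.23 | 0.26 |

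At a true 5%, the values for d = 5% and 10% still round to the plan's 0.02.

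**What counting these patients in the stage rules would do.** If 25% was meant for evaluable patients, the all-treated rate is 25% × (1 − d) = 23.75%, 22.5% or 20%. Power then falls from 0.76 to 0.72, 0.68 or 0.58.

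**The case against.** The strongest reply is that this is a stated choice. ORR and both stage sizes are in the same unit, response-evaluable patients. If the 5% and 25% hypotheses refer to such patients, alpha and power are correct. That stands. It leaves one point open: the reported ORR does not describe all treated patients, and nothing else in the plan does so for response.

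The second reply is that few patients fall in the gap, and this largely stands too. Re-evaluation is not defined as a scan. The flowsheet in 5.0 has disease documented on day 1 of each cycle and again 4 weeks after treatment ends, and 10.4 has all patients seen at that visit. The note to Table 3 asks sites to document objective progression after a stop for symptomatic deterioration. These steps bring most deteriorating patients back into the evaluable set. They do not help a patient who dies or is lost before any of them, and none of them alters the denominator rule.

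Third, early deaths are not hidden: PFS counts death as an event and OS is described (13.3). That is true, but neither corrects ORR.

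A reader might go further and infer three things that the documents do not support:
- **That the type I error of the design is wrong.** This needs both replacement and hypotheses set for all treated patients. The plan states neither.
- **That the gap spans the 12 weeks before the first scan.** Clinical documentation of disease starts earlier.
- **That the ovarian result shows the problem at work.** Section 2.3 reports 7/19 responses after the cohort reached its goal of 20. The reason for the missing patient is not given. The difference is 7/19 = 36.8% against 7/20 = 35.0%, and the decision is the same. One cohort closed to initial accrual at 20 with 19 in the denominator does not suggest replacement either.

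**Conclusion.** The concern holds in a limited form. Applied as written, 8.1.2 and 13.2 remove certain non-responders from the primary denominator, so the bias in ORR has a known direction. Its size is a factor of 1/(1 − d): x1.05 to x1.25 over an assumed d of 5% to 20%, or about one percentage point for one patient dropped from 4/20. Given the narrow gap, the low end of that range is more plausible, but the documents give no figure that settles it. The shift is small beside the width of the confidence intervals in cohorts of this size.

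The design calculations are correct for evaluable patients. A rise in P(active) at a true 10%, from 0.13 to 0.15, 0.17 or 0.23, is conditional on replacement and on an all-treated reading of the hypotheses. This is a cheap improvement to reporting and does not invalidate the stage decisions.

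**What to change.** In 13.2, add for every cohort, including those already accrued:
- ORR with its exact 95% confidence interval on all eligible treated patients, beside the evaluable ORR. Patients who die, or stop for clinical progression or symptomatic deterioration, before re-evaluation count as non-responders.
- A listing of each patient excluded from the evaluable set, with the reason.

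Leave the 0/10 and 4/20 stage rules unchanged for cohorts already assessed. Changing the decision set after responses in at least one cohort are known would be a post-hoc change to the primary analysis of an open-label trial, and could cost power as shown above.

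The cost is a slightly lower second ORR figure and a little more analysis work. No extra patients, visits or scans are needed.
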